### 5.2. Safety Analysis Periods

For the safety analysis, the following analysis periods for post-baseline data are defined. Safety data in these periods are considered treatment-emergent.

- Weeks 0-12 placebo-controlled phase: This period encompasses data through Week 12. It starts on the date of the first dose of IP in the study, and ends on the date before IP dispensing at Week 12 for subjects who receive at least 1 dose of IP after Week 12 (defined as the date of the last dose of IP in the study no earlier than the date of IP dispensing at Week 12), or 28 days after the last dose of IP in the study or on the date of the actual last follow-up in the study, whichever comes first, for subjects who discontinue at or prior to Week 12.

Of note, this period is exclusive of the date of the first dose of IP in the study and inclusive of the date of IP dispensing at Week 12 for the analyses of the lab, vital signs, weight, and ECG data.

The safety analysis tables for the placebo-controlled phase will be presented by the following 4 groups: placebo, APR 30 BID, APR 40 BID, and APR total.

- Weeks 0-52 apremilast-exposure period: This period encompasses all apremilast-exposure data through Week 52, irrespective of when the apremilast exposure starts (at Week 0 or 12) in the study. It starts on the date of the first dose of apremilast in the study, and ends on the date before IP dispensing at Week 52 for subjects who receive at least 1 dose of apremilast after Week 52 (defined as the date of the last dose of apremilast in the study no earlier than the date of IP dispensing at Week 52), or 28 days after the last dose of apremilast in the study or on the date of the actual last follow-up in the study, whichever comes first, for subjects who discontinue at or prior to Week 52.

Of note, this period is exclusive of the date of the first dose of apremilast in the study and inclusive of the date of IP dispensing at Week 52 for the analyses of the lab, vital signs, weight, and ECG data.

The safety analysis tables, with an exception for the summaries of labs, vital signs, and body weight by time point, for the apremilast-exposure period during Weeks 0-52 will be presented by the following 4 groups: APR 30 BID, APR 40 BID, APR 30 BID/APR 40 BID, and APR total, as follows:

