- The APR 30 BID group includes the data during the APR 30 BID treatment for subjects who receive APR 30 BID only in the study, subjects who initially receive APR 30 BID and switch to APR 40 BID at Week 12, and subjects who initially receive placebo and switch to APR 30 BID at Week 12.
- The APR 40 BID group includes the data during the APR 40 BID treatment for subject who receive APR 40 BID only in the study and subjects who initially receive placebo and switch to APR 40 BID at Week 12.
- The APR 30 BID/APR 40 BID group includes the data during the APR 40 BID treatment for subjects who initially receive APR 30 BID and switch to APR 40 BID at Week 12.
- The APR total group combines all the data of all the groups.

For the summaries of labs, vital signs, and body weight by time point, the data during the APR 30 BID and APR 40 BID treatments after Week 12 for subjects who initially receive

placebo and switch to APR 30 BID and APR 40 BID, respectively, at Week 12 will be summarized in the placebo/APR 30 BID and placebo/APR 40 BID groups, respectively.

- Weeks 0-104 apremilast-exposure period: This period encompasses all apremilast-exposure data through Week 104, irrespective of when the apremilast exposure starts (at Week 0 or 12) in the study. It starts on the date of the first dose of apremilast in the study, and ends 28 days after the last dose of apremilast in the study or on the date of the actual last follow-up in the study, whichever comes first.

Of note, this period is exclusive of the date of the first dose of apremilast in the study for the analyses of the lab, vital signs, weight, and ECG data.

The treatment groups presented in the safety analysis tables for the apremilast-exposure period during Weeks 0-104 will be the same as those for the apremilast-exposure period during Weeks 0-52.

- Weeks 52-104 apremilast-exposure period: This period encompasses the apremilast-exposure data during Weeks 52-104 and is to be summarized for subjects who receive at least 1 dose of apremilast after Week 52 (defined as the date of the last dose of apremilast in the study no earlier than the date of IP dispensing at Week 52). It starts on the date of IP dispensing at Week 52, and ends 28 days after the last dose of apremilast in the study or on the date of the actual last follow-up in the study, whichever comes first.

Of note, this period is exclusive of the date of IP dispensing at Week 52 for the analyses of the lab, vital signs, weight, and ECG data.

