### 12.1. Adverse Events

AEs will be coded according to the MedDRA. Unless otherwise specified, AEs will be summarized by SOC and PT, with SOCs sorted in the standard international order and PTs within each SOC in descending order of subject incidence.

For the analyses of AEs, the following point estimates are provided, unless otherwise specified:

- Subject incidence: Subject incidence (i.e., percentage [%] used in a frequency summary) is defined as the number of subjects with the specific event divided by the number of subjects included in the analysis. Subjects with multiple occurrences of the specific event in the specific analysis period will be counted only once in the numerator.
- Exposure-adjusted incidence rate (EAIR) per 100 person-years: The EAIR per 100 person-years is defined as 100 times the number of subjects with the specific event divided by the total exposure time (in years) to the event among subjects included in the analysis. Subjects with multiple occurrences of the specific event in the specific analysis period will be counted only once in the numerator. The exposure time for a subject without the specific event is the duration of the specific analysis period as described in Section 5.2, whereas the exposure time for a subject with the specific event is the duration of the specific analysis period up to the start date (inclusive) of the first occurrence of the specific event. The total exposure time in years is calculated by dividing the sum of exposure time in days over all subjects included in the analysis by 365.25. The EAIR per 100 person-years is interpreted as the expected number of subjects with at least 1 occurrence of the specific event per 100 person-years of exposure to the event.

A subject data listing of all AEs (including treatment-emergent AEs [TEAEs] and non-TEAEs) will be provided.

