#### 12.1.2. All TEAEs

All TEAEs will be summarized by SOC and PT as well as by PT only (in descending order of subject incidence) for the Weeks 0-12 placebo-controlled phase, the Weeks 0-52, Weeks 0-104, and Weeks 52-104 apremilast-exposure periods.

All TEAEs by exposure interval will be summarized for the Weeks 0-12 placebo-controlled phase and the Weeks 0-104 apremilast-exposure period. The exposure intervals are ≤ 2, > 2 – 4, > 4 – 8, > 8 weeks for the Weeks 0-12 placebo-controlled phase, and ≤ 2, > 2 – 4, > 4 – 12, > 12 – 20, > 20 – 28, > 28 – 36, > 36 – 44, > 44 – 52, > 52 – 68, > 68 – 86, > 86 weeks for the Weeks 0-104 apremilast-exposure period. Each subject is counted once in the numerator of a subject incidence or EAIR for each applicable specific TEAE in each exposure interval where an event starts. The denominator of a subject incidence is the number of subjects with the exposure time reaching the lower bound of the particular exposure interval, and the denominator of an EAIR is the sum of the exposure time during the exposure interval (up to the start date [inclusive] of the first occurrence of the specific event for each subject reporting the event in the interval) among the same number of subjects as in the denominator of the corresponding subject incidence.

All TEAEs will be summarized by sex and concomitant use of oral corticosteroids for the Weeks 0-12 placebo-controlled phase and the Weeks 0-104 apremilast-exposure period.

All TEAEs starting after the date of the last dose of IP and up to 28 days after the last dose of IP will be summarized for subjects who enter the observational follow-up phase during the Weeks 0-12 placebo-controlled phase and the Weeks 0-104 apremilast-exposure period. The EAIR will not be provided in this summary.

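### The exposure-adjusted AE rate uses whole-period person-time, but SAP 5.2 splits a 30-to-40 mg switcher between two columns, so as written the rates in both columns are too low.

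*SAP*

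**What the plan says.** For a subject with no event, SAP 12.1 states: "The exposure time for a subject without the specific event is the duration of the specific analysis period as described in Section 5.2". For a subject with an event, "the exposure time for a subject with the specific event is the duration of the specific analysis period up to the start date" of the first occurrence.

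SAP 5.2 describes the Weeks 0-52 period by subject, whatever the dose: "It starts on the date of the first dose of apremilast in the study, and ends on the date before IP dispensing"; for those who continue, the dispensing meant is the Week 52 one. The Weeks 0-104 period has the same start and "ends 28 days after the last dose of apremilast in the study or on the date of the actual last follow-up", whichever is first. Neither is cut at the Week 12 dose change.

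The same section then splits the data by dose. "The APR 30 BID group includes the data during the APR 30 BID treatment", and this covers subjects who later move to 40 mg. Their later data go to another column: "The APR 30 BID/APR 40 BID group includes the data during the APR 40 BID treatment for subjects who initially receive APR 30 BID"; these are the Week 12 switchers. The Weeks 0-104 tables use the same columns.

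For the exposure-interval tables, SAP 12.1.2 takes as the subject-incidence denominator "the number of subjects with the exposure time reaching the lower bound of the particular exposure interval". The interval EAIR sums person-time over those same subjects.

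**The concern.** The numerator follows the dose being taken and the denominator follows the calendar period. A switcher's 40 mg events cannot be counted in APR 30 BID, but the 40 mg weeks still count there as exposure. In the 30/40 column the mismatch runs the other way: the first 12 weeks count as exposure although events in them belong to APR 30 BID.

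Long-term safety at the two doses is a secondary objective (SAP 3.2), and the EAIR is the summary meant to make unequal follow-up comparable. Switching is built into the design, because 30 mg subjects without a 20% fall in total Mayo score at Week 12 move to 40 mg (SAP 4.1). The dilution would therefore affect two of the three dose columns over Weeks 0-52 and leave APR 40 BID untouched.

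**Working it through.** **Plan figures.** The documents give no EAIR, person-time or number of switchers, so there is no plan figure to reproduce. The 55 per arm comes from SAP 4.4.

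**Assumptions.** 27.5 placebo subjects are re-randomized to 30 mg (equal split assumed). There is no dropout, and events are rare. The number of switchers, k, is a share of the 55; the documents do not give it, so a range is shown.

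**One event-free switcher, Weeks 0-52.**
- As written: 52 weeks in APR 30 BID plus 52 in APR 30 BID/APR 40 BID = 104 weeks.
- On treatment: 12 + 40 = 52 weeks.

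**APR 30 BID column, Weeks 0-52.**
- As written: 55 × 52 + 27.5 × 40 = 3960 weeks. Multiplied by 7 and divided by 365.25, this is 75.9 person-years (PY).
- Matched to the dose: (55 − k) × 52 + k × 12 + 27.5 × 40.

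| Switch share | k | Matched weeks | Matched PY | Matched / written | EAIR too low by |
|---|---|---|---|---|---|
| 10% | 5.5 | 3740 | 71.7 | 0.944 | 6% |
| 30% | 16.5 | 3300 | 63.2 | 0.833 | 17% |
| 40% | 22 | 3080 | 59.0 | 0.778 | 22% |
| 50% | 27.5 | 2860 | 54.8 | 0.722 | 28% |

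**APR 30 BID/APR 40 BID column, Weeks 0-52.** Every switcher contributes 52 weeks where 40 apply: 40/52 = 0.769, or 23% low whatever the switch share.

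**Commoner events.** A constant-hazard calculation with the same counts, treating a switcher whose only event is on 40 mg as event-free in APR 30 BID, gives for switch shares of 10% to 50%:
- at 5 to 10 events per 100 PY, APR 30 BID is 6% to 28% low and the 30/40 column 23% to 24% low;
- at 200 per 100 PY, APR 30 BID is 7% to 32% low and the 30/40 column 37% low.

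**Weeks 0-104, everyone followed to Week 104** (an upper bound on follow-up, with no dose change in the Extension). At 5 to 10 events per 100 PY, APR 30 BID is 6% to 32% low. The 30/40 column is only 12% to 13% low, because the 12 misplaced weeks are set against a longer period (12/104 = 11.5% in the rare-event limit).

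**Exposure-interval tables.** At 40% switching, the >12-20 week denominator in APR 30 BID is 55 + 27.5 = 82.5 subjects as written, but 82.5 − 22 = 60.5 are still on 30 mg. Since 60.5/82.5 = 0.733, subject incidence in that interval is 27% low. In the 30/40 column, the intervals up to Week 12 would carry full denominators with no possible events.

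**Other text that might settle it.** Treatment duration (SAP 9.1) is also defined by period, not dose. Elsewhere the SAP does handle the Week 12 boundary: LOCF is not carried across the switch (11.2.3.1), and compliance is summarized separately for Weeks 0-12 and 12-52 (9.2). The EAIR has no such rule.

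**The case against.** The strongest reply is that a coherent reading without bias exists. SAP 12.1 refers to Section 5.2, where the column rule is part of each period's description. If exposure counts among the data that 5.2 splits, a switcher gives 12 + 40 = 52 weeks, and APR total, which combines the columns, adds up. The literal reading gives 104 weeks for 52 weeks of treatment. This reply shows what was probably intended. It does not settle the text: 12.1 names the duration of the period, not the column's data, and no other section splits exposure time.

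The size is also not fixed by the documents. A 10% switch share gives only 6% for APR 30 BID, and dropout matters. If switchers averaged 20 weeks on 40 mg (assumed) at 40% switching, as-written exposure is 33 × 52 + 22 × 32 + 1100 = 3520 weeks against 3080. APR 30 BID is then 12.5% low instead of 22%, although 30/40 worsens to 12/32 = 37.5% low. This objection stands, and the percentages are illustrations.

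A reader might infer two stronger things that the documents do not support.

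- **That only the 30 mg side is affected, so 30 mg is made to look safer than 40 mg.** The 30/40 column holds 40 mg data and is itself about 23% low, more than APR 30 BID at 30% switching (17%). The distortion in favor of 30 mg holds only against the APR 40 BID column.
- **That the error grows over Weeks 0-104.** It shrinks for 30/40 and need not grow for APR 30 BID. Extension entry requires a Mayo endoscopy score of 1 or less at Week 52, which Week 12 non-improvers may meet less often. If 40% switch, and 10% of switchers and 50% of the others enter (assumed; doses unchanged in the Extension), the ratio is 4653/5647 weeks, or 18% low against 22% for Weeks 0-52. Under the current protocol Extension subjects receive 30 mg BID, so a switcher who enters can again contribute 30 mg data.

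**Conclusion.** The point holds on the text as written. SAP 12.1 and 5.2 together give EAIRs that are too low in APR 30 BID and in APR 30 BID/APR 40 BID, and the interval denominators in 12.1.2 are inflated in the same way, including those for subject incidence. Under the stated assumptions, APR 30 BID over Weeks 0-52 is about 6% low at 10% switching and 17% to 28% low at 30% to 50%; 30/40 is about 23% low at any share. Dropout and Extension entry change these sizes.

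Not affected: Weeks 0-12; APR 40 BID over Weeks 0-52; placebo-to-apremilast subjects, whose period starts at their first apremilast dose; APR total, if each subject's time is counted once; and overall subject incidence, which uses no person-time. Safety is descriptive (SAP 12), so no test changes. The wording should still be settled before programming, because two readings of it give rates that can differ by a fifth or more.

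**What to change.** In SAP 12.1 and 12.1.2, define exposure time in each treatment column as the part of the analysis period whose data Section 5.2 assigns to that column:

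- For switchers, APR 30 BID time ends the day before Week 12 dispensing, and APR 30 BID/APR 40 BID time starts on the Week 12 dispensing date.
- Each segment ends at the next dose change or at the end of the Section 5.2 period. The last segment keeps the window of up to 28 days after the last dose, since events there are treatment-emergent; cutting at the last dose would keep those events and drop their person-time.
- Within a segment, exposure stops at the first event in that segment. This also settles how to treat a switcher whose first occurrence was on 30 mg, which the SAP leaves open for the 30/40 column.
- The same split applies to any Extension dose change under the current protocol.
- In APR total, each subject's person-time is counted once.

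The cost is SAP wording and a programming change. No new data are needed.

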#### 12.1.1. Overall Summary of TEAEs

An overall summary of the following TEAE categories will be provided for the Weeks 0-12 placebo-controlled phase, the Weeks 0-52, Weeks 0-104, and Weeks 52-104 apremilast-exposure periods:

- Any TEAE
- Any drug-related TEAE

- Any severe TEAE
- Any serious TEAE
- Any serious drug-related TEAE
- Any TEAE leading to drug interruption
- Any TEAE leading to drug withdrawal
- Any TEAE leading to death

In addition, the overall summary of TEAE categories will be provided by age category (< 65, ≥ 65), race (white, non-white), and region (North America, Western Europe, Eastern Europe/Russia, Australia/New Zealand) for the Weeks 0-12 placebo-controlled phase and the Weeks 0-104 apremilast-exposure period.

#### 12.1.2. All TEAEs

All TEAEs will be summarized by SOC and PT as well as by PT only (in descending order of subject incidence) for the Weeks 0-12 placebo-controlled phase, the Weeks 0-52, Weeks 0-104, and Weeks 52-104 apremilast-exposure periods.

All TEAEs by exposure interval will be summarized for the Weeks 0-12 placebo-controlled phase and the Weeks 0-104 apremilast-exposure period. The exposure intervals are ≤ 2, > 2 – 4, > 4 – 8, > 8 weeks for the Weeks 0-12 placebo-controlled phase, and ≤ 2, > 2 – 4, > 4 – 12, > 12 – 20, > 20 – 28, > 28 – 36, > 36 – 44, > 44 – 52, > 52 – 68, > 68 – 86, > 86 weeks for the Weeks 0-104 apremilast-exposure period. Each subject is counted once in the numerator of a subject incidence or EAIR for each applicable specific TEAE in each exposure interval where an event starts. The denominator of a subject incidence is the number of subjects with the exposure time reaching the lower bound of the particular exposure interval, and the denominator of an EAIR is the sum of the exposure time during the exposure interval (up to the start date [inclusive] of the first occurrence of the specific event for each subject reporting the event in the interval) among the same number of subjects as in the denominator of the corresponding subject incidence.

All TEAEs will be summarized by sex and concomitant use of oral corticosteroids for the Weeks 0-12 placebo-controlled phase and the Weeks 0-104 apremilast-exposure period.

All TEAEs starting after the date of the last dose of IP and up to 28 days after the last dose of IP will be summarized for subjects who enter the observational follow-up phase during the Weeks 0-12 placebo-controlled phase and the Weeks 0-104 apremilast-exposure period. The EAIR will not be provided in this summary.

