- Subjects who were randomized to placebo at baseline will be re-randomized to receive apremilast (30 mg BID or 40 mg BID) and will be dose-titrated in 10-mg/day increments over the first 8 days of treatment (Table 5).

Subjects who do not achieve at least a 20% decrease from baseline in the TMS at Week 12 will receive the following IP until the Week 52 Visit:

- Subjects who were randomized to apremilast 30 mg BID at baseline will be re-assigned apremilast 40 mg BID, with no dose titration.
- Subjects who were randomized to apremilast 40 mg BID at baseline will continue to receive apremilast 40 mg BID.
- Subjects who were randomized to placebo at baseline will be re-randomized to receive apremilast (30 mg BID or 40 mg BID) and will be dose-titrated in 10-mg/day increments over the first 8 days of treatment (Table 5).

In order to maintain the blind for the treatment assigned at baseline, all subjects will receive blister cards of identical appearance during the titration period beginning at Week 12. However, for subjects continuing on the dosage of apremilast assigned at baseline, and for subjects who are not undergoing dose titration (as noted above), the IP included in the “titration” portion of the blister card will include the total daily dose of apremilast (30 or 40 mg BID) and will not include the dose titration.

Extension Phase

At the end of the Blinded Active-treatment Phase (Week 52), subjects who have a Mayo endoscopy score ≤ 1 will have the opportunity to participate in the Extension Phase. Subjects participating in the Extension Phase will receive apremilast for an additional 52 weeks (Weeks 52 to 104). With the implementation of Amendment 4, subjects entering the Extension Phase will receive apremilast 30 mg BID. Subjects currently in the Extension Phase who are receiving apremilast 40 mg BID will be switched to 30 mg BID at the next scheduled visit.

Post-treatment Observational Follow-up Phase

All subjects are required to spend 4 weeks in the Post-treatment Observational Follow-up Phase following the last dose of IP.

Study Population

The study population consists of female and male subjects 18 years and older at the time of signing the informed consent form (ICF). The major eligibility criteria are:

- Diagnosis of UC with a duration of at least 3 months, prior to the Screening Visit
- TMS ≥ 6 to ≤ 11 prior to randomization in the study (Section 6.7)
- Mayo endoscopic subscore ≥ 2 prior to randomization in the study

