## 9. EXTENT OF EXPOSURE TO INVESTIGATIONAL PRODUCT

### 9.1. Treatment Duration

Treatment duration will be summarized for the Weeks 0-12 placebo-controlled phase using the safety population, for the Weeks 0-52 and Weeks 0-104 apremilast-exposure periods using the apremilast subjects as treated population, and for the Weeks 52-104 apremilast-exposure period for subjects who receive at least 1 dose of apremilast after Week 52.

Treatment duration (in weeks) is calculated as (the date of the last dose of IP in the period – the date of the first dose of IP in the period + 1) / 7 and rounded to one decimal place. The date of the last dose of IP in the Weeks 0-12 placebo-controlled phase is defined as the date before IP dispensing at Week 12. The date of the last dose of IP in the Weeks 0-52 apremilast-exposure period and the date of the first dose of IP in the Weeks 52-104 apremilast-exposure period are defined as the date before and the date of, respectively, IP dispensing at Week 52.

Treatment duration will be summarized as a continuous variable, and as a categorical variable with the following exposure intervals:

- Weeks 0-12 placebo-controlled phase:  $\leq 4$ ,  $> 4 - 8$ ,  $> 8 - 12$ ,  $> 12$  weeks
- Weeks 0-52 apremilast-exposure period:  $\leq 4$ ,  $> 4 - 8$ ,  $> 8 - 12$ ,  $> 12 - 20$ ,  $> 20 - 28$ ,  $> 28 - 36$ ,  $> 36 - 44$ ,  $> 44 - 52$ , and  $> 52$  weeks
- Weeks 0-104 apremilast-exposure period:  $\leq 4$ ,  $> 4 - 8$ ,  $> 8 - 12$ ,  $> 12 - 20$ ,  $> 20 - 28$ ,  $> 28 - 36$ ,  $> 36 - 44$ ,  $> 44 - 52$ ,  $> 52 - 68$ ,  $> 68 - 86$ ,  $> 86 - 104$ ,  $> 104$  weeks
- Weeks 52-104 apremilast-exposure period (intervals denote the number of weeks relative to the date of the first dose of IP in the Weeks 52-104 apremilast-exposure period as defined above):  $\leq 16$ ,  $> 16 - 34$ ,  $> 34 - 52$ ,  $> 52$  weeks

A subject data listing of study drug records will be provided.

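### The Weeks 0-104 TEAE-by-exposure-interval table counts up to 28 days after the last dose as exposure, which dilutes the crude subject incidence in the >52-68 week interval

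*SAP*

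**What the plan says.** SAP 12.1 defines the exposure time behind the adverse event estimates: "The exposure time for a subject without the specific event is the duration of the specific analysis period as described in Section 5.2". For a subject with the event, the time stops at the first occurrence.

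SAP 5.2 starts the Weeks 0-104 apremilast-exposure period at the first apremilast dose, "irrespective of when the apremilast exposure starts (at Week 0 or 12) in the study". The period "ends 28 days after the last dose of apremilast in the study or on the date of the actual last follow-up in the study", whichever is earlier. Safety data in the period, including the post-dose days, count as treatment-emergent.

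SAP 12.1.2 plans all TEAEs by exposure interval. The late intervals are "> 44 – 52, > 52 – 68, > 68 – 86, > 86 weeks for the Weeks 0-104 apremilast-exposure period". The rule for the percentage is: "The denominator of a subject incidence is the number of subjects with the exposure time reaching the lower bound of the particular exposure interval". It does not require the subject to be on drug. For the exposure-adjusted incidence rate (EAIR), "the denominator of an EAIR is the sum of the exposure time during the exposure interval", taken over the same subjects.

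The Protocol (Summary and Section 4.1) limits continuation at Week 52: only subjects with a Mayo endoscopy score of 1 or less "will have the opportunity to participate in the Extension Phase". All subjects have 4 weeks of follow-up after the last dose.

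SAP 9.1 has a separate on-drug measure: "Treatment duration (in weeks) is calculated as (the date of the last dose of IP in the period" minus the first dose date, plus 1), divided by 7. The by-interval table does not use it.

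**The concern.** Long-term safety is a secondary objective, and this table is the planned display of how adverse event incidence changes with time on apremilast. Its interval cut at 52 weeks coincides with the visit at which some subjects stop by design. For a subject treated from Week 0 who stops there, the 28-day tail is enough to carry the subject over the cut.

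The percentage counts such a subject as one whole unit at risk for a 16-week interval, although only about 4 weeks are observed and those follow the end of treatment. Even with a constant on-drug hazard, the percentage would then fall right after Week 52. Protocol 1.4.2 reports that the commonest events occur mostly in the first weeks of treatment, so an artefactual late fall would look believable.

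**Working it through.** The plan gives no figure for this table, so there is none to reproduce. The check has three parts.

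**1. Who falls in which interval.** Inputs: first apremilast dose on Day 1 or, for placebo switchers, about Day 85; Week 52 target Day 365 (SAP 5.3.1: week × 7 + 1); visit window ±3 days (Protocol Table 4); last dose on the day before the visit; tail of 28 days (SAP 5.2).

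- *Apremilast from Week 0, no Extension:* on drug 364 days = 52.0 weeks (51.6-52.4 over the window). Adding 28 gives 392 days = 56.0 weeks (55.6-56.4). With a follow-up visit 21 days after the last dose, the total is still 55.0 weeks. The subject is in >52-68 with about 56 − 52 = 4 of 16 weeks observed.
- *Placebo switched at Week 12, no Extension:* on drug 364 − 84 = 280 days = 40.0 weeks. Adding 28 gives 308 days = 44.0 weeks (43.1-44.9 over the visit windows). The subject is in >36-44 by right, having been on drug beyond 36 weeks. Only the tail can carry the subject to the >44-52 bound, and never to 52 weeks.
- *Anyone else:* a subject who stops within 28 days before any interval bound is carried into the next interval off drug. The Weeks 0-12 period has the same 28-day tail for early discontinuers.

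**2. Direction.** Let p be the on-drug incidence over 16 weeks at constant hazard, r the off-drug to on-drug hazard ratio, and s the off-drug share of the denominator.

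Reported incidence = (1 − s)p + s[1 − (1 − p)^(r/4)]

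The second bracket equals p at r = 4. The percentage is therefore too low for r < 4 and too high only for r > 4.

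**3. Size.** These inputs are assumptions, not figures from the documents: 110 Week 0 starters (2 × 55 planned); about 50 placebo switchers; a proportion c = 0.7 of Week 0 starters reaching Week 52; a proportion f of completers entering the Extension; p = 10%; one continuous exposure clock; the pooled apremilast column; and every entrant observed for the full interval.

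- On drug = 110cf + 50(c/0.9)f. At f = 0.5: 38.5 + 19.4 = 57.9.
- Off drug = 110c(1 − f) = 38.5, so s = 38.5/96.4 = 0.40.
- Off-drug incidence over 4 weeks at r = 1: 1 − 0.9^(1/4) = 2.6%.
- Reported = (57.9 × 0.10 + 38.5 × 0.026)/96.4 = 7.0%, against 10% on drug.

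The last two columns show reported incidence, with relative bias in brackets:

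| Extension entry f | off-drug share s | r = 1 | r = 0 |
|---|---|---|---|
| 0.3 | 0.61 | 5.5% (−45%) | 3.9% (−61%) |
| 0.5 | 0.40 | 7.0% (−30%) | 6.0% (−40%) |
| 0.7 | 0.22 | 8.4% (−16%) | 7.8% (−22%) |

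The proportion c cancels from the relative bias.

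*EAIR in the same scenarios.* A non-entrant adds only about 4 weeks to the denominator, and tail events count in the numerator. At r = 1 the ratio to the true rate is 1.00 for every f. At r = 0 it is 0.71 (f = 0.3) to 0.93 (f = 0.7). At r = 2 it is 1.29 to 1.07.

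**The case against.** **The tail is a convention, and events and time match.** Events in the 28 days are treatment-emergent under SAP 5.2, so including both the days and the events is coherent. This stands for the EAIR, which uses only accrued time. It does not rescue the percentage, which gives a subject seen for 4 weeks the same weight as one seen for 16.

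**A reader might infer that late incidence is understated throughout the table.** The documents do not support that. The EAIR is unbiased at equal hazard. Nothing in the plan shows whether the off-drug event rate of non-entrants, who include those with an endoscopy score above 1, is lower or higher than on drug. The direction is firm only for the crude percentage.

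**A reader might also infer that placebo switchers suffer the same fault in >36-44.** They do not: they belong there on drug. Their marginal interval is >44-52, and the visit window decides which of them reach it.

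**An undiluted late estimate already exists.** The SAP 5.2 Weeks 52-104 period is limited to subjects dosed after Week 52, and SAP 12.1.1 to 12.1.7 report most TEAE categories for it. This stands and limits the harm. Those summaries run on study time, include former placebo subjects with about 40 weeks of prior exposure, and are not split by exposure interval, so they do not replace the affected cell.

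**The size is assumed.** This also stands. The SAP further leaves open whether the clock restarts for subjects moved from 30 to 40 mg BID. If it restarts, those who stop at Week 52 reach only about 44 weeks and drop out of the >52-68 cell, so the dilution would differ from the table above.

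**Conclusion.** The concern holds in a limited form. Under SAP 12.1, 5.2 and 12.1.2 read together, Week 0 apremilast starters who complete Week 52 and do not continue are counted whole in the >52-68 week denominator with about 4 of 16 weeks observed, essentially off drug. The crude subject incidence in that interval is understated unless the off-drug hazard is about four times the on-drug hazard or more. At equal hazard the understatement is 16% to 45% for 70% down to 30% Extension entry, given a 10% 16-week incidence and one continuous clock in the pooled column. The direction below the fourfold threshold follows from the rules under a constant hazard; the size rests on those assumptions.

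The point does not show that the EAIR is biased in a known direction, nor that the long-term safety assessment as a whole is unsound. Safety is summarised without inferential testing, and the Weeks 52-104 summaries exclude non-entrants. Severity is minor: one descriptive safety table, cheaply corrected.

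**What to change.** In SAP 12.1.2, for the by-interval table only:

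- Define exposure as on-treatment time, from first to last dose of apremilast (of investigational product for Weeks 0-12).
- Count a subject in an interval only if dosed beyond its lower bound. For Week 0 starters in >52-68, also require at least one apremilast dose after Week 52, as SAP 5.2 already defines it.
- Cut numerators and EAIR time at the last dose. Keep later TEAEs in the overall tables and in the post-last-dose table that SAP 12.1.2 already plans.
- State whether the exposure clock restarts for subjects switched from 30 to 40 mg BID.

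Replacing the exposure definition with SAP 9.1 duration alone is not enough. Completers have 51.6-52.4 weeks on drug, so some still reach the 52-week bound with almost no observed time. If a share q of the 38.5 non-entrants does so, and their tail events are removed, the bias is −38.5q/(57.9 + 38.5q). That is −17% at q = 0.3, −25% at q = 0.5 and −30% at q = 0.65, so the last of these is no better than the current rule at equal hazard. The Week 52 dosing condition closes this gap.

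The cost is a few sentences in the SAP and a changed end date and inclusion flag in one program. The downside is that TEAEs in the 28-day tail leave this one table.
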